# 8.3.3. Vital Signs

Absolute values and changes from baseline will be summarized for the following parameters.

- Systolic Blood Pressure (mmHg)
- Diastolic Blood Pressure (mmHg)
- Pulse Rate (bpm)
- Body Temperature (°C)

All data will be listed.

### 8.3.4. 12-Lead ECGs

Absolute values and changes from baseline will be summarized for the following parameters.

- Heart Rate (bpm)
- PR (msec)
- QRS (msec)
- QT (msec)
- QTcF (msec)
- QTcB (msec)

The percentage of subjects with 12-lead ECG values outside pre-defined limit will be summarized.

All data will be listed.

# 8.3.5. Physical Examinations

[figure not shown]
Physical examination will be listed.

### 8.4. Pharmacokinetics Evaluation

Pharmacokinetics evaluation will be made on the PK population.

# 8.4.1. Serum MT-2990 Concentration

Serum MT- 2990 concentrations will be summarized at each nominal sampling point (Table 14.4.1). All serum concentrations will also be listed.

Statistical Analysis Plan	Mitanhishi Tanaha Dhamana Danahamana Amaniga Ina
Protocol No. MT-2990-A01	Mitsubishi Tanabe Pharma Development America, Inc.
9.5.2 Dhammandemanias Frakratic	·
8.5.2. Pharmacodynamics Evaluation	
Pharmacodynamics evaluation will be	made on the PD population.

### 9. DATA PRESENTATION CONVENTIONS'

# 9.1. Number of Digits to Report

# (1) Non-PK related

Statistic	Specification	Apply to
Minimum, Maximum	Same number of DPs as the	All original (i.e. non-
	data provided in the datasets	derived)
	See section 7.1	Derived
Mean, Median, SD, SE,	One more DP than above	All
Confidence intervals		
Percentages*1	1 DP	All
Ratios	3 DPs	All
p-values*2	3 DPs	All

\*1 Percentages: use 1 place beyond the decimal point, except for the following cases:

If the percentage is equal to 0, then leave blank, do not use (0)

If the percentage is equal to 100, then use "(100)" without a decimal

If the p-value is less than 0.001, then use p<0.001

Note: DPs for specific parameters are regarded as follows.

[PARAMCD (Conversion factor)]

- 2 DPs

CHOL (0.02586), HDL (0.02586), LDL (0.02586), TRIG (0.01129), PHOS (0.3229), UREAN (0.357)

- 1 DP

GLUC (0.0555), BILDIR (17.1), BILI (17.1)

- Integer

**CREAT (88.4)** 

[figure not shown]
# (2) PK Serum Concentration

Statistic	Specification
Individual value	4 significant digits
Minimum, Maximum	4 significant digits
Mean, SD, Median	4 significant digits

# 9.2. Treatments to Report

Treatment	For TFLs
Placebo	Placebo
MT-2990	MT-2990

\*2 p-values: use 3 places beyond the decimal point, except for the following cases:

# (2) Safety

Analysis Visit	Apply to		
	Laboratory Tests	Vital Signs	12-Lead ECGs
Baseline	X	X	X
Week 1	X	X	
Week 2	X	X	·
Week 4	X	X	
Week 8	X	X	
Week 12 (EOT)	X	X	
Week 13	X	X	
Week 16	X	X	X
Week 27			
Week 38 (EOS)			

Unscheduled visits will not be displayed in by-visit summary tables but will be included in the data listings.

In by-visit summary tables for interim safety assessment, limited analysis visits will be reported. The first interim safety assessment will report baseline to Week 2. The second interim safety assessment will report baseline to Week 4. The third interim safety assessment will report baseline to Week 16. All visit will be included in the data listing.

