8.5 Withdrawal of Individual Subjects

A subject will be withdrawn if ANY of the following criteria are met:

- The subject wishes to withdraw from further participation
- The subject is significantly noncompliant with the Protocol
- Continuing in the study would be detrimental to the subject's safety in the opinion of the Investigator, eg, the subject experiences a pretreatment event (PTE) or an AE that requires early termination (ET) because continued participation poses an unacceptable risk to the subject's health, or the subject is unwilling to continue because of the PTE or AE
- Subjects who become pregnant during the study should be withdrawn from study treatment. Refer to Section 12.9 for necessary documentation and procedures for following up with the subject
- Subjects who develop:
 - Hypersensitivity reactions, such as anaphylaxis and moderate to severe infusion-related reactions.
 - Abnormal hematologic indices as below:
 - White blood cell count (WBC) < 3000/mm3 (< 3.0×10^9 /L) or absolute neutrophil count < $1.500/\mu$ L
 - Platelets < 100,000/μL
 - Hemoglobin < 8 g/dL

Note: If a subject has a decline of hemoglobin to < 9 g/dL, hemoglobin will be repeated within 2 weeks.

- ALT or AST > 5 times ULN
- ALT or AST > 3 times ULN sustained for more than two weeks
- ALT or AST > 3 times ULN AND total bilirubin > 2 X ULN or international normalized ratio > 1.5

Note: If a subject experiences elevated ALT or AST \geq 3 times ULN, liver tests (ALT, AST, bilirubin, ALP, gamma-glutamyl transferase, and creatinine kinase) will be repeated within 3 to 5 days.

In addition, a subject may be withdrawn at any time for reason(s) other than those listed here. Medical monitor should be notified for all withdrawals.

If a subject is withdrawn prematurely from the study, the date the subject is withdrawn from the study and the reason for withdrawal will be recorded in the electronic Case Report Form (eCRF).

In case of withdrawal of a subject, the ET assessments should be performed per Table 2.

Reporting events as a SAE must be considered in cases where the AE has led to a withdrawal or the withdrawal is for a safety reason and, therefore, may be medically important, in

accordance with Section 12.

Any unresolved AE or SAE will be followed up according to Section 12.10.

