#### 6. STATISTICAL CONSIDERATIONS

### 6.1. Descriptive Statistics

### (1) Non-PK related

Continuous data will be summarized descriptively using the number in the analysis set (N), the number of observations (n), mean, standard deviation (SD), median, minimum and maximum. Categorical data will be summarized using frequency counts and percentages. The denominator for the percentages will be the total number of subjects in the treatment group or analysis population being presented, unless otherwise specified.

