# (2) Other endpoints

The analysis visits will be defined as following.

Analysis visit	Nominal day	Window
Baseline	Day 1	NA
Week 1	Day 8	Day 2 to 11
Week 2	Day 15	Day 12 to 20
Week 4	Day 29	Day 21 to 43
Week 8	Day 57	Day 44 to 71
Week 12 (EOT)	Day 85	Day 72 to 88
Week 13	Day 92	Day 89 to 99
Week 16	Day 113	Day 100 or after
Week 27	Day 190	NA
Week 38 (EOS)	Day 267	NA

EOT assessment data will be included as visit data in the applicable window.

The date of the first dose of study drug is defined as Day 1. If the data at Day 1 is missing, the last data before Day 1 will be used for baseline. If one visit corresponds to both window of

week 12 and 13, the visit will be applied an analysis visit which matches visit on case report form (CRF). For other visits, if there are multiple data in a window, the closest data to nominal day will be used. If more than one data in the window with the same distance to the nominal day, the data of later date will be used. For Week 27 and 38, CRF visit will be used as analysis visits.

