# 8.3.2. Laboratory Tests

Absolute values and changes from baseline will be summarized for the following laboratory tests parameters.

Laboratory Test	Parameters		
Hematology	Hemoglobin*, Hematocrit*, Platelet count*, Red blood cell (RBC)		
	count*, Reticulocyte count*, Mean corpuscular hemoglobin (MCH),		

	Mean corpuscular hemoglobin concentration (MCHC), Mean corpuscular volume (MCV), White blood cell (WBC) count and differential
Biochemistry	Alkaline phosphatase (ALP) *, Aspartate aminotransferase (AST) *, Alanine aminotransferase (ALT) *, Gamma-glutamyl transpeptidase (GGT) *, Potassium*, Sodium*, Chloride*, Inorganic phosphate, Glucose*, Urea, Bilirubin (direct and total) *, Cholesterol*, Triglycerides*, High density lipoprotein-cholesterol (HDL-C) *, Low density lipoprotein-cholesterol (LDL-C) *, Protein (total) *, Albumin*, Creatine kinase*, Creatinine*
Coagulation	Prothrombin time*, International normalized ratio*, Activated partial thromboplastin time*
Urinalysis	Specific gravity, pH*, protein*, glucose*, ketones*, urobilinogen*, haemoglobin

Only the parameters with \* will be summarized for interim safety assessment.

Shift table for urinalysis will be generated if it is needed.

All data will be listed.

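### The visible SAP plans no count per arm of women who met the Protocol 8.5 laboratory limits, and its by-visit tables leave out unscheduled results

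*SAP*

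**What the plan says.** Protocol 8.5 sets laboratory limits at which an individual woman is withdrawn. They cover white cells, neutrophils, platelets and hemoglobin, and three liver criteria: ALT or AST above 5 x ULN; "ALT or AST > 3 times ULN sustained for more than two weeks"; and ALT or AST above 3 x ULN combined with a bilirubin or INR limit. The same section calls for liver tests to be repeated 3 to 5 days after ALT or AST reaches 3 x ULN, and hemoglobin within 2 weeks of a fall below 9 g/dL.

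On reporting, SAP 8.3.2 says "Absolute values and changes from baseline will be summarized for the following laboratory tests parameters". SAP 6.1 fixes the statistics for continuous data as the number in the analysis set, "the number of observations (n), mean, standard deviation (SD), median, minimum and maximum". The only categorical laboratory output is conditional and confined to urine: "Shift table for urinalysis will be generated if it is needed". SAP 9.3 says "Unscheduled visits will not be displayed in by-visit summary tables", and the same sentence keeps those values in the listings. SAP 7.3 adds that "if there are multiple data in a window, the closest data to nominal day will be used".

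The ECG is treated differently. SAP 7.1.3.2 lists QTcF limits, and SAP 8.3.4 says "The percentage of subjects with 12-lead ECG values outside pre-defined limit will be summarized".

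SAP 8.3.2 also limits the interim laboratory summaries to asterisked parameters. White-cell count and differential carry no asterisk.

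**The concern.** Liver injury and cytopenia appear as a few extreme values in individual women. The natural summary is how many women in each arm crossed a stated limit at any time. The protocol already has the limits, yet the visible SAP does not tabulate against them. The repeat tests that Protocol 8.5 calls for fall outside the visit schedule, so a peak or confirmatory value can be missing from every laboratory table.

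At stake is whether an imbalance between arms can be read from a planned table or must be assembled by hand from listings. This matters most at the three interim safety assessments, which SAP 4.3 says serve to decide whether the study stops for safety.

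**Working it through.** **Plan figures.** The documents give no figure for laboratory threshold counts, so there is none to reproduce on this point. The arm size used below comes from SAP 3.3: 28 evaluable per arm and 25% drop-out give 28 / (1 - 0.25) = 37.3, rounded up to 38, as stated.

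**Limits against planned tables.**

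| Protocol 8.5 criterion | What a by-visit table can show | What it cannot show |
|---|---|---|
| Single-value limits (blood counts; ALT or AST above 5 x ULN) | Minimum or maximum shows at least one crossing at that scheduled visit | How many women crossed; whether extremes at two visits belong to one woman or two |
| ALT or AST above 3 x ULN for more than two weeks | High maxima at successive visits | Whether the same woman stayed high |
| ALT or AST with bilirubin or INR | High maxima in separate parameter tables | Whether they occurred in the same woman |

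The last two rows need values linked within a subject. No per-parameter, per-visit statistic supplies that.

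**Path of a repeat value.** The Week 4 window in SAP 7.3 runs from Day 21 to Day 43, with nominal Day 29. Assume a scheduled sample on Day 29 gives ALT 3.2 x ULN and the repeat on Day 33 gives 5.5 x ULN.
- Under SAP 9.3 the repeat is unscheduled and stays out of the table.
- Under SAP 7.3 the Day 29 value is closer to nominal and is the one used.
- Either way the tabulated maximum for this woman is 3.2, and her crossing of 5 x ULN appears only in the listing.

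**Size, with assumed values.** Suppose k of 38 women have ALT 5.5 x ULN at a scheduled visit and the rest 0.5 x ULN. The visit mean is (5.5k + 0.5(38 - k)) / 38.

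| k | Mean (x ULN) | Maximum (x ULN) | Count table |
|---|---|---|---|
| 1 | 24/38 = 0.63 | 5.5 | 1/38 = 2.6% (exact 95% CI 0.1 to 13.8) |
| 2 | 29/38 = 0.76 | 5.5 | 2/38 = 5.3% (0.6 to 17.7) |
| 3 | 34/38 = 0.89 | 5.5 | 3/38 = 7.9% (1.7 to 21.4) |

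The maximum reveals the crossing but is the same in all three rows. The mean moves by 5.0/38 = 0.13 x ULN per woman.

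**Comparison with the ECG.** The safety visit table in SAP 9.3 has one post-baseline visit for ECG (Week 16) and seven for laboratory tests (Weeks 1, 2, 4, 8, 12, 13 and 16). Only the ECG gets a threshold count.

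**Interim tables.** Hemoglobin, platelets, ALT, AST, bilirubin and INR are asterisked. White-cell count and differential, which supply two of the parameters limited in Protocol 8.5, are not, so the interim tables would not summarize them.

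**The case against.** A reader might infer several stronger things that the documents do not support.

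- **That laboratory data are tabulated only as means.** They are not. Minimum and maximum are planned, so a crossing at a scheduled visit is visible.
- **That unscheduled values are lost.** SAP 9.3 and 8.3.2 keep them in listings, and about 76 women is few enough for a hand count. The value that triggers a repeat may also come from a scheduled sample and so be in the table already: at 3 x ULN against an assumed 0.5, it moves the mean by (3.0 - 0.5)/38 = 0.07 x ULN and can set the maximum.
- **That no table can reflect a crossing.** Meeting a limit calls for withdrawal, with the reason recorded in the eCRF. SAP 8.1.1 summarizes disposition, and SAP 8.3.1 tabulates serious TEAEs and those leading to discontinuation.
- **That the data monitoring committee would not see such cases.** Protocol 13.1 gives it AE and SAE lists monthly and lets it ask for more. Its charter is not among the documents.
- **That the SAP contradicts the protocol.** Protocol 14.3.4.4 promises only summaries by arm and planned sampling point, and the SAP delivers those. The 8.5 limits are rules for individual withdrawal, not endpoints.

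All of this stands, and it limits the point. It does not remove it. Listings permit a count, but none is planned. The disposition and TEAE routes are indirect: under Protocol 12.6 an abnormal value becomes an AE only if the investigator judges it clinically significant, and a related diagnosis is recorded in place of the value. Counts by preferred term are therefore not tied to the 8.5 limits.

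**Conclusion.** The point holds as a reporting gap. The visible SAP plans by-visit descriptive statistics that exclude unscheduled values, and no count per arm of women ever meeting the Protocol 8.5 laboratory limits. Applied literally, its rules can leave a peak or confirmatory value out of every laboratory table, and they cannot show the sustained or joint liver criteria by arm. The interim tables also omit white cells and neutrophils.

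The actual size cannot be computed from the documents. The percentages above rest on assumed ALT values and 38 women per arm, and they show only what a count adds to a maximum.

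One reservation remains. The SAP abbreviation list defines ULN, the visible text never uses it, and parts of the SAP are redacted. A ULN-based summary in removed text cannot be fully excluded. The hint is weak, because the contents list shows only adverse events and 12-lead ECGs under 7.1.3.

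This is a worthwhile, inexpensive improvement to safety reporting in a proof-of-concept study. It is not an error that undermines the planned analysis.

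**What to change.** In SAP 7.1.3, add pre-defined limits for laboratory tests that take over the existing Protocol 8.5 criteria unchanged. In SAP 8.3.2, add one table on the Safety population giving, by arm, the number and percentage of subjects who met each criterion at any time after first dose, from scheduled and unscheduled results. Produce it at each of the three interim safety assessments and at the Week 16 lock. Include white cells and neutrophils in the interim versions whatever their asterisk status.

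The cost is one table from data already collected, in a format the SAP already uses for QTcF, plus two programming rules. The first defines how persistence beyond two weeks is derived from dated results. The second concerns the joint liver criterion: its mix of AND and or can be grouped in more than one way, and the sponsor must clarify the intended grouping from its own protocol text before programming. Neither rule requires a change to clinical management.

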7.2.1 Risk:Benefit Statement

Treatment of moderate to severe pain related to endometriosis is a significant unmet need. Young women at childbearing age develop endometriosis related pain and other complications which effects their productivity at peak age.

The current study will evaluate the effect of MT-2990 on treatment of moderate to severe endometriosis related pain. This study will evaluate if MT-2990 may treat the endometriosis related pain.

MT-2990 is a human IgG1 monoclonal antibody that highly and specifically binds to IL-33 among IL-1 family molecules. It is under investigation for the potential clinical benefits for the treatment of moderate to severe endometriosis-related pain in women with surgically diagnosed endometriosis.

[figure not shown]
The overall nonclinical safety data and profile is supportive of the clinical use of MT-2990 in human clinical trials. Nonclinical studies have demonstrated no significant toxicity of MT-2990.

In the 1 clinical study conducted to date, single doses of MT-2990 were considered to be safe and well tolerated in healthy male subjects. No deaths, SAEs, AEs leading to withdrawal, or severe TEAEs occurred during the study.

The Sponsor will undertake all reasonable measures, to minimize the risk to subjects. Subjects will receive no further dosing if they meet any of the withdrawal criteria listed in Section 8.5.

This study will provide additional efficacy and safety information on the risk:benefit profile of MT-2990.

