# 4.3. Data Monitoring Committee (DMC)

An independent DMC, composed of experts in the management of subjects with the disease under study will be established for MT-2990-A01 according US FDA guidance. An independent biostatistician will be assigned to the DMC to maintain the integrity of the study blind and provide safety data at regular predefined intervals during the study and provide the interim safety assessments to the DMC.

The primary purpose of this committee will be to review safety data for the protection of subject safety (including infusion site reactions, hypersensitivity and immune system disorders such as allergic reaction, anaphylaxis, cytokine release syndrome, etc).

There will be 3 interim safety assessments as described in section 4.1. The planned interim safety assessments will be conducted to determine whether the study will be stopped due to safety concerns.

A DMC charter will outline the scope and key responsibilities, timing of reviews, communications between the DMC and the Sponsor, and recommendations and action rules for

the study.

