### (2) Treatment Compliance

The subjects are supposed to take a dose every four weeks and totally 4 doses per protocol. Treatment compliance (%) =number of doses/ROUNDUP(treatment duration/28).

[figure not shown]

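### The visit cut-offs on the interim safety tables leave the first two DMC reviews without a by-arm laboratory summary from any visit after the second-dose visit; this matters mainly at the second review

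*SAP*

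**What the plan says.** SAP 9.3, part (2) Safety, sets the rule: "In by-visit summary tables for interim safety assessment, limited analysis visits will be reported". It then fixes the range for each review. For the earliest it reads "The first interim safety assessment will report baseline to Week 2"; for the next, which matters most here, "The second interim safety assessment will report baseline to Week 4"; and for the last of them, "The third interim safety assessment will report baseline to Week 16". The paragraph ends with "All visit will be included in the data listing". The visit table just above it schedules laboratory summaries at baseline and Weeks 1, 2, 4, 8, 12, 13 and 16. Unscheduled visits go to listings only.

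On dosing, SAP 7.1.1.2 states: "The subjects are supposed to take a dose every four weeks and totally 4 doses per protocol". Protocol 10.18.2 measures vital signs after infusion at Visits 2, 5, 6 and 7, and Protocol 7.1.1 equates Visit 7 with Week 12. The infusions are therefore on Day 1 and at Weeks 4, 8 and 12.

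SAP 4.1 triggers the three reviews when 20 women have finished Week 2, when half have finished Week 4, and when half have finished Week 16. SAP 4.3 gives their purpose: "The planned interim safety assessments will be conducted to determine whether the study will be stopped due to safety concerns".

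On earlier exposure, Protocol 7.2.1 says: "In the 1 clinical study conducted to date, single doses of MT-2990 were considered to be safe and well tolerated in healthy male subjects". Protocol 7.2 describes the present trial as giving multiple doses.

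**The concern.** A trigger decides when a review takes place. Here the same week also limits what the by-visit tables may show. Women enrolled early will have passed the trigger visit by the time of the review, and the rule leaves their later laboratory results out of the tables although they have been collected.

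The omitted visits are those after repeat dosing, which has no precedent in the earlier human study. Laboratory values also matter to this protocol: section 8.5 withdraws women on defined blood count and liver test thresholds. A small shift across one arm, below the level at which any one woman's result stands out, is hard to find in subject listings and easier to see in means or medians by arm. The DMC would make two of its three decisions on whether to stop without that view.

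**Working it through.** **Step 1. Doses against tabulated laboratory visits**

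| Review | Laboratory visits tabulated | Visits later than the second-dose visit (Week 4) |
|---|---|---|
| First | Weeks 1, 2 | none |
| Second | Weeks 1, 2, 4 | none |
| Third | Weeks 1, 2, 4, 8, 12, 13, 16 | Weeks 8, 12, 13, 16 |

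The Week 4 window in SAP 7.3 runs from Day 21 to Day 43, but the value nearest Day 29 is used, and that is ordinarily the Week 4 visit itself. The window therefore does not bring in data from well after the second dose.

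**Step 2. The number behind the 50% triggers**

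Protocol 14.1 gives 28 per arm for a difference of 0.5, SD 0.65, two-sided 5%, two-sample t-test. The exact calculation gives n = 27.5, so 28, with power 80.7%. With 25% drop-out, 28 / 0.75 = 37.3, so 38 per arm and 76 in total. The plan's figure reproduces, and 50% is 38 women.

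**Step 3. Accrual (assumed)**

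The synopsis estimates first enrolment in December 2018 and last completion in February 2020, taken here as about 62 weeks. If completion means Week 38, accrual lasts W = 62 − 38 = 24 weeks. If it means Week 16, W = 62 − 16 = 46 weeks. Assume an even rate and no drop-out:

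- r = 76 / W = 3.17 per week (W = 24) or 1.65 per week (W = 46).
- A review triggered by k women finishing Week w occurs at t = k/r + w.
- Women who have reached Week v by then: r(t − v) = k − r(v − w), kept between 0 and 76.

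**Step 4. Results**

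| Quantity | Formula | W = 24 | W = 46 |
|---|---|---|---|
| First review, Week 8 reached | 20 − 6r | 1.0 | 10.1 |
| First review, Week 12 reached | 20 − 10r | 0 | 3.5 |
| Second review, Week 8 reached | 38 − 4r | 25.3 | 31.4 |
| Second review, Week 12 reached | 38 − 8r | 12.7 | 24.8 |
| Second review, Week 16 reached | 38 − 12r | 0 | 18.2 |
| Third review, randomized | 38 + 16r, at most 76 | 76 | 64.4 |
| Third review, Week 12 reached | 38 + 4r | 50.7 | 44.6 |

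With 1:1 allocation, the Week 8 column at the second review would hold about 13 to 16 women per arm (25.3 / 2 to 31.4 / 2).

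**Step 5. Sensitivity**

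Taking the calendar as 61 weeks (W = 23 or 45) gives about 24 to 31 women at Week 8 at the second review. At an assumed 1 woman per week the figures are 38 − 4 = 34 at the second review and 20 − 6 = 14 at the first.

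**The case against.** The strongest reply is that nothing is withheld. The same SAP paragraph puts all visits in the listings. Under Protocol 13.1 the DMC gets adverse event lists monthly and SUSARs in real time, and may ask for further information. Protocol 12.6 has clinically significant laboratory abnormalities recorded as adverse events, or under the related diagnosis, so signals of clinical weight reach those monthly lists. The adverse event summaries in SAP 8.3.1 are not by-visit tables and have no stated visit limit; they cover the reactions that SAP 4.3 names as the committee's main concern. A charter, not among these documents, may add more. All of this stands. A reader might infer that the DMC cannot see repeat-dose laboratory data at its first two reviews; the documents do not support that.

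A reader might also infer that the second review is the last that can protect the women enrolled. That does not follow either. At the third review, on the same model, 76 − 50.7 = 25.3 to 76 − 44.6 = 31.4 of the 76 planned women have not reached the Week 12 infusion (in the slower case about 12 of them are not yet randomized). At 1 woman per week only 38 + 16 = 54 would be randomized by then. Monthly lists continue between reviews.

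Nor does the point extend to vital signs: these are also taken 15, 30 and 60 minutes after the Week 4 infusion (Protocol 10.18.2).

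Finally, matching each cut-off to its trigger visit gives columns with largely complete denominators, which is a coherent choice. That explains the rule, but it is a weak reason to leave out later columns that could be shown with their n.

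**Conclusion.** The point holds as a limited one about laboratory tables. At the first two reviews the DMC has no by-arm laboratory summary from a visit after the second-dose visit. The effect is small at the first review (about 1 to 10 women with Week 8 results) and material at the second (about 25 to 31 with Week 8 results and 13 to 25 with Week 12 results, in listings only). Priority is low to moderate.

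It rests on these assumptions:

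- The Week 4 sample is drawn before the infusion. The schedule of assessments is not available to confirm this. A later draw would show only the immediate period after the second dose, so the substance would change little.
- The interim tables are split by arm, as Protocol 14.3.4.4 provides for safety summaries generally.
- The counts assume even accrual and no drop-out, from planned dates. They are illustrative: the current protocol is dated 4 March 2020, after the estimated completion, so the calendar is uncertain.

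**What to change.** In SAP 9.3 (2), replace the three sentences that set the Week 2, Week 4 and Week 16 limits, and adapt the sentence introducing them, with: *At each interim safety assessment the by-visit summary tables will report every analysis visit with data at the cut-off, by treatment group, with n per visit.* Leave the triggers in SAP 4.1 and the asterisked parameter list in SAP 8.3.2 as they are.

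The cost is one SAP sentence and removal of a visit filter from the interim table programs, with no new data, visits or staff. The downside is that some later-visit columns will have small n and incomplete denominators; printing n makes this visible. The documents do not say which reviews have already taken place, and the change helps only those still to come.
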